10.3.1 Primary endpoint

The primary endpoint is defined in Section 4.3.1.

The estimand for the primary endpoint for patients with haemophilia A will be addressed comparing the number of treated bleeds between the randomised arms (arm 1 and 2) based on the FAS including information obtained from the restart of the trial to when the patient permanently discontinues treatment or completes the confirmatory analyses cut-off using negative binomial regression, where the patients' number of bleeds will be analysed with treatment and bleeding frequency (<9, ≥ 9 bleeding episodes during the past 24 weeks prior to screening) as factors, and logarithm of exposure time as offset. The estimated ratio of ABR between the treatment regimens (concizumab prophylaxis and no prophylaxis) with corresponding 95% confidence interval, p-value for the test for superiority and also estimates of the actual ABRs with corresponding 95% confidence intervals in each treatment arm will be presented. The primary analysis will also account for the different intercurrent events as described under the estimand.

The analysis of the primary endpoint for patients with haemophilia B will be done in a similar way as described for haemophilia A patients.

Sensitivity analysis

Several sensitivity analyses will be implemented by haemophilia type to further investigate the different assumptions that goes into the above estimand and statistical methodology. Note that some of these sensitivity analyses are implemented by altering the strategy for a given intercurrent event and hence addresses a slightly different estimand.

- In order to investigate the missing at random (MAR) assumption, a tipping point analysis will be implemented where patients that permanently discontinue treatment before 24 weeks for arm 1 or before 32 for arm 2 will be modelled with an increasing bleeding rate until the conclusion of superiority is changed. Those patients that permanently discontinues treatment before 24 weeks for arm 1 or before 32 weeks for arm 2 will have the offset period fixed at 24 or 32 weeks, respectively. Any patient that permanently discontinues treatment before the confirmatory analyses cut-off but after 24 weeks for arm 1 or after 32 weeks for arm 2 will not be considered to have missing data for the purpose of this tipping point analysis.
- In order to investigate the effect of excluding observed data a model where all intercurrent events will be handled by use of the treatment policy strategy will be fitted. The model will be similar to the primary analysis but where the patient's bleeds and observation time collected post permanent treatment discontinuation (the first intercurrent event) and collected during periods with use of factor products not related to treatment of a bleed (the third intercurrent event) will be used. This analysis will be performed using the FAS.
- In order to not rely on the model assumptions of the primary analysis a non-parametric Van Elteren test to compare the mean ABR in the two randomised groups will be done. This is done using the FAS including information obtained from the restart of the trial to when the patient permanently discontinues treatment or completes the confirmatory analyses cut-off.

• In order to investigate the impact of the initial randomisation prior to the clinical pause, the primary analyses will be re-run where patients from the initial randomisation are included. For patients randomised to on-demand all information from the point of the initial randomisation to the time of restart will be included. For patients randomised to the initial concizumab regimen all information collected from the time of randomisation until treatment discontinuation will be included.

Further sensitivity analyses can be specified in the SAP.

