6.4 Randomisation criteria

To be randomised into arm 1 or arm 2 in this trial, one of following randomisation criteria must be answered "yes".

Randomisation criteria:

- 1. On-demand patient transferred from NN7415-4322 (explorer 6)
- 2. On-demand patient who has ≥5 documented treated bleeds in the last 24 weeks or ≥10 treated bleeds during 52 weeks before screening.

Version: Status: 52 of 138 Page:

Final

7 **Treatments**

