9.1.3 Haemophilia Treatment and Bleed History

The following information on haemophilia treatment and bleed history 12 months prior to screening should be recorded in the eCRF:

- Type of treatment/regiment
 - o Prophylaxis or on-demand
 - Start date
 - o Stop date
- Number of bleeding episodes
 - o If possible, specify number of spontaneous bleeding episodes.
- Coagulation factor product(s)
 - Brand name, or if the brand is not known, the type of product, (plasma derived or recombinant)
- Dosage used for prophylaxis (for prophylaxis patients only)
- Dosing frequency during prophylaxis (for prophylaxis patients only)
- Approximate dose to treat a bleeding episode
- Approximate number of doses to treat a bleeding episode

Page:

63 of 138

9.1.4 **Target Joints**

All current target joints, including number of bleedings during the last 12 months, must be registered. A target joint is defined as three or more spontaneous bleeds into a single joint within a consecutive 6-month period. Where there have been ≤ 2 bleeds into the joint within a consecutive 12-month period the joint is no longer considered a target joint. Surgical joint bleeds should not be included in the target joint count.

Following information will be collected in the eCRF:

- Location
- Position (left/right)
- Number of bleeding episodes the last 12 months

9.2 **Efficacy assessments**

Planned time points for all efficacy assessments are provided in the flowchart in Section $\underline{2}$.

9.2.1 **eDiary**

Novo Nordisk will provide the patient with an eDiary for electronic recording of following assessments:

- Treatment with concizumab, see Section 9.2.2
- Bleeding episodes including treatment of bleeds, see Section 9.2.3
- PRO questionnaires see Section 9.2.6
- Health economic questions see Section 9.8

The eDiary and related support services will be supplied by a vendor working under the direction and supervision of Novo Nordisk.

Patients or patient's caregiver will be trained in the use of the eDiary by the investigator or delegated personnel before entering of any data. The eDiary will be dispensed to the patient at visit 2a (unless an eDiary has already been dispensed). After visit 2a and onwards, data will be entered by the patient or patient's caregiver in the eDiary at home. The patient should bring his eDiary at all visits to ensure the eDiary is working properly. The eDiary will be returned by the patient at the end of trial visit (visit 27a).

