10.1 Sample size determination

The estimand for the primary objectives will for patients in arms 1 and 2 be addressed based on the Full Analysis Set (FAS; see Section 10.2) using negative binomial regression.

The sample size calculation has been determined based on the estimand for the primary and confirmatory secondary objectives. In the below calculations it is assumed that the treatment duration is 24 weeks for patients in arms 1 and 32 weeks for patients in arm 2. For the comparison of previous PPX to concizumab PPX in arm 4 it is assumed that the treatment duration is 38 weeks (estimated from NN7415-4322 (explorer 6)) on the previous PPX regimen and 24 weeks on the concizumab maintenance dose.

When evaluating the power of the negative binomial analysis with exposure time as offset and treatment as factor, annual bleeding rates of 24 and 18 are assumed for the no-prophylaxis HA patients, and the no-prophylaxis HB patients, respectively. An ABR of 3-5 is expected for concizumab prophylaxis. Assuming further a yearly over-dispersion of 13, the power for concluding superiority of concizumab prophylaxis versus no-prophylaxis for HA patients becomes at least 82% with 21 patients (14 in the concizumab arm and 7 in the comparator arm). The power for concluding superiority of concizumab prophylaxis versus no prophylaxis for HB patients becomes at least 79% with 33 patients (22 in the concizumab arm and 11 in the comparator arm). When evaluating the power of the negative binomial analysis (with exposure time as offset and treatment as factor and incorporating within-subject repeated measurements using an unstructured covariance matrix) with respect to showing non-inferiority of concizumab prophylaxis vs previous prophylaxis in a withinpatient comparison the assumptions are: Concizumab ABR of 3-5, an ABR for previous prophylaxis of 4, a noninferiority margin of 2.0 on the relative scale, a sample size of 30 and a yearly over-dispersion of 13, and a patient's frailty for experiencing bleeds in the first period (on previous PPX) and the second period (on concizumab PPX) is fully correlated. With these assumptions the power will be at least 79% to show non-inferiority for each haemophilia subtype.

ABR assumptions

Based on the available studies and sources, a representative mean ABR on on-demand treatment for the severe haemophilia A patients of 24 bleeds/year and for the haemophilia B patients of 18 bleeds/year is considered appropriate (see Table 15).

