10.3 Statistical analyses

The statistical analysis plan (SAP) was updated prior to the first patient restarting the trial to reflect the changes made in protocol amendment #4, and includes a more technical and detailed elaboration of the statistical analyses.

As described in Section 5, several evaluations will be made prior to the end of this trial. This section will describe the analyses of the primary and the secondary confirmatory endpoints at the confirmatory analyses cut-off focusing on the randomised arms as well the within-subject comparison in arm 4 of the confirmatory secondary endpoints.

The bleed rate is defined as the number of treated bleeds over the respective observation periods. As a general rule, a treated bleed is defined as any bleed where a factor-containing product is reported between the start and stop time of a bleed. Multiple bleeding locations occurring at the same time point will be counted as one bleeding episode. Further, the endpoints will not include re-bleed. A re-bleed is defined as a bleeding episode (worsening of bleeding site conditions e.g. swelling, pain) starting within 72 hours after stopping treatment of a previous treated bleeding episode (or re-bleed) at the same anatomical location. Note that there can be more than one re-bleed related to the same bleed. If a bleeding episode occurs in the same location more than 72 hours after stopping treatment of a previous bleeding episode or re-bleed in the same location, the bleed is defined as a new bleeding episode.

The Type-I error for testing the two confirmatory hypotheses related to bleeds will be preserved by using hierarchical testing. The tests will be evaluated separately for the two patient populations, i) patients with haemophilia A and ii) patients with haemophilia B. The conclusion from the trial will be drawn for each of the two populations separately, i.e. the conclusion from one population does not influence the conclusion from the other population. Correction for multiplicity between the two populations is therefore not considered relevant. The type 1 error will be controlled for the two hypothesis within one population, as described below.

The overall significance level is 5%. If a hypothesis is confirmed, the significance level will be reallocated to the next hypothesis in the hierarchy and then that hypothesis will be tested at the 5% significance level. This process will be repeated until no further hypotheses can be confirmed.

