The primary endpoint is analysed using negative binomial regression. Superiority of concizumab prophylaxis over no prophylaxis in the patient population will be concluded if the two-sided 95% confidence interval of the treatment ratio is below 1.

If superiority is concluded for the primary endpoint the confirmatory secondary hypothesis will be tested with a significant level of 5%. The confirmatory secondary hypothesis aims at comparing the

Page:

89 of 138

bleeding rate during concizumab treatment with the bleeding rate on the patients' previous prophylaxis.

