5.3 Primary endpoint analysis

Refer to SAP for confirmatory analyses cut-off version 5.

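### Should the primary arm 1 versus arm 2 model adjust for the actual pre-trial bleed count instead of the <9/≥9 category?

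*Protocol*

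**What the plan says.** Protocol Section 10.3.1 fits the primary model separately in HA and HB. Its terms are treatment, the <9/≥9 history category and log exposure: "bleeding episodes during the past 24 weeks prior to screening) as factors, and logarithm of exposure time as offset". Section 7.2 makes the same split, together with haemophilia type, the stratification factor for randomisation to arms 1 and 2. Success means that "the two-sided 95% confidence interval of the treatment ratio is below 1" (Section 10.3).

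Section 9.1.3 collects more detail than the model uses: "The following information on haemophilia treatment and bleed history 12 months prior to screening should be recorded in the eCRF". The number of bleeding episodes is on that list. Section 6.4 sets a floor but no ceiling on history for on-demand patients who do not transfer from explorer 6: "On-demand patient who has ≥5 documented treated bleeds in the last 24 weeks or ≥10 treated bleeds during 52 weeks before screening".

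The power statement in Section 10.1 rests on a simpler model, a "negative binomial analysis with exposure time as offset and treatment as factor". The only SAP supplied is the 56-week descriptive one. For the primary analysis its Section 5.3 says: "Refer to SAP for confirmatory analyses cut-off version 5". That document is not among those supplied.

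**The concern.** Splitting a count at a cut-point discards information. The upper category is open-ended, so patients with 9 and with 30 prior bleeds get the same adjustment. Variation between patients is the main source of noise, and Table 2 plans only 8 HA and 12 HB controls. A count that costs nothing to obtain might narrow the interval for the ABR ratio, yet neither the primary model nor any sensitivity analysis listed in Section 10.3.1 uses it. If history predicted on-trial bleeding well, the plan would be giving up precision in its most important comparison.

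**Working it through.** **Inputs (Protocol Section 10.1 unless noted).** ABR 24 (HA) or 18 (HB) on demand, and 5 on concizumab, the case behind the stated minimum power. Exposure 24 versus 32 weeks. Yearly over-dispersion 13, read as variance divided by mean of the one-year count. Powered numbers 7+14 (HA) and 11+22 (HB). Two-sided 5% level (Section 10.3). The correlation between pre-trial and on-trial bleeding tendency is **not given for arms 1 and 2**, so I took 0 to 0.8 as an assumed range. Table 17 uses 1.0 and 0.8, but only for arm 4.

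**Step 1: reproduce the stated power.** With dispersion k = (13 − 1)/ABR, k is 12/24 = 0.50 (HA control), 12/18 = 0.67 (HB control) and 12/5 = 2.40 (concizumab). The variance of the log rate in an arm is (1/n) × [1/(ABR × t) + k].

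- HA: control (1/7)(1/11.08 + 0.50) = 0.0843; concizumab (1/14)(1/3.08 + 2.40) = 0.1946; SE = √0.2790 = 0.528. Power = Φ(|ln(5/24)|/0.528 − 1.96) = Φ(1.01) = 84.4%.
- HB: 0.0715 + 0.1239 = 0.1954; SE 0.442. Power = Φ(|ln(5/18)|/0.442 − 1.96) = Φ(0.94) = 82.6%.

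Simulating the fitted model (4,000 runs) gives 81.8% and 78.0%, against 82% and 79% in the plan. The stated power therefore holds with no covariate at all.

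**Step 2: what the planned category already gives.** I drew pre-trial counts at the on-demand rate, applied the Section 6.4 threshold and used stratified 1:2 allocation. At correlation 0.8 the category raises power from 83.3% to 94.8% (HA) and from 80.2% to 94.3% (HB).

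**Step 3: replace the category with the log 12-month count.** Empirical SD of the log rate ratio at the powered numbers (2,500 runs); variance change = (new SD/old SD)² − 1:

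| Correlation | HA SD | HA variance | HB SD | HB variance |
|---|---|---|---|---|
| 0 | 0.567 → 0.578 | +4% | 0.470 → 0.475 | +2% |
| 0.5 | 0.543 → 0.553 | +4% | 0.453 → 0.441 | −5% |
| 0.8 | 0.508 → 0.462 | −17% | 0.423 → 0.379 | −20% |

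At the randomised numbers (8+16 and 12+24), with the entry threshold applied to all or half of the patients, the change is +1% to −7% at 0.3 and 0.5, and −17% to −23% at 0.8. A further run at over-dispersion 13 gives HA SD 0.517 → 0.535 at 0.3 and 0.522 → 0.524 at 0.5; for HB, 0.446 → 0.450 and 0.435 → 0.434. Below 0.8 the change is small and its sign is not stable. Keeping both terms removes the gain at 0.5 (HA +6% or +2%, HB +4% or +1%).

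**Step 4: is the estimate still aimed at the estimand?** Section 4.2 targets the ratio of ABRs between the regimens. The plan's over-dispersion gives the arms unequal dispersion (0.50 versus 2.40 in HA), and covariate adjustment then moves the log ratio away from ln(5/24) = −1.57. At 0.8 the HA bias is −0.19 with the category and −0.31 with the count. As multipliers on the ratio these are e^−0.19 = 0.83 and e^−0.31 = 0.73, so the count flatters concizumab more.

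Root mean squared error combines bias and spread. For HA at 0.8 it goes from 0.516 to 0.539. The implied SDs are √(0.516² − 0.19²) = 0.480 and √(0.539² − 0.31²) = 0.441, a variance fall of about 15% that the extra bias more than cancels. HB goes from 0.436 to 0.449. In that run the error was slightly worse at every correlation tried. In the runs at the randomised numbers, mean squared error changed by between +4% and −7%. Neither result is a dependable gain.

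**Step 5: power and type I error.** For HA at 0.5 the count lifts power from 90.6% to 93.1%, yet the true SD rises (0.543 → 0.553) while the median reported SE falls (0.492 → 0.470). That increase is not precision. Under a simulated null at 0.5 and 0.8, two-sided rejection at the powered numbers is 7.9–9.4% (category) versus 8.2–9.5% (count) in HA, and 6.9–7.3% versus 6.9–7.8% in HB. At the randomised numbers it is 7.3–8.2% versus 7.4–7.5% (HA) and 6.6–7.6% versus 6.5–7.1% (HB). The two models are about equally liberal.

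**The case for a change.** The best case for the count is that the upper category covers most patients and is wide. Requiring a 24-week count of at least 5 under the plan's own rates, about 69% (HA) and 61% (HB) fall in it, with a 10th to 90th percentile range of about 10–27 and 9–25 bleeds. The count is already collected, so the change costs only wording. If dispersion were equal in the two arms, the bias in Step 4 would disappear and the variance reduction of 17–23% at correlation 0.8 would be real.

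The description stands, and so does the conditional gain. Its conditions are not in the plan. The value 0.8 is stated for prophylaxis against prophylaxis in the same arm 4 patients. Equal dispersion is not what an over-dispersion of 13 implies at ABRs of 24 and 5.

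The collected count may also predict less well than simulated. It is retrospective, Section 9.1.3 does not restrict it to treated bleeds, and that section also records regimen start and stop dates, so the regimen may have changed within the 12 months.

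A count model as an extra sensitivity analysis would do no harm. Section 10.3.1 leaves room for more in the SAP, and the confirmatory SAP may already hold one. Its absence from the protocol list changes no conclusion.

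**Conclusion.** The concern does not hold. The primary model adjusts for baseline bleeding through the factor used to stratify randomisation, and the stated power neither uses nor needs a finer covariate. Replacing the factor with the 12-month count brings about nothing at a correlation of 0.5 or below. At 0.8 it exchanges roughly 15 to 23% less variance for a larger shift away from the ABR ratio, with no dependable gain in total error. Statisticians could reasonably choose either model, so the plan's choice is not an error.

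A swap would also come late. The 56-week SAP, dated August 2022, treats the confirmatory within-patient comparison as finished (Section 5.5.1). That comparison comes after the primary test in the hierarchy, so the primary analysis had presumably been run. Changing its covariate now would be post hoc in an open-label trial.

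These figures rest on reading over-dispersion 13 as a variance-to-mean ratio in each arm, on history drawn at a constant on-demand rate, and on an assumed correlation range. The confirmatory SAP version 5 was not available to check.

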- **Intercurrent events**: 1) permanent treatment discontinuation, 2) temporary treatment discontinuation, 3) use of factor-containing products not related to treatment of a bleed (see Section 5.2.1) and 4) minor surgery.
- Target patient population: HA patients previously treated on demand before entering the trial.

The same five components apply for the estimand for HB patients where HA in the target patient population is substituted with HB.

Utilizing these five components, the estimand for the primary objectives can be described as the treatment ratio of the ABRs for treated spontaneous or traumatic bleeding episodes up until the confirmatory analyses cut-off between the two randomised treatment regimens in the target patient population while patients are adhering to the allocated treatment regimen.

The strategies for how to account for the intercurrent events in the primary estimand are as follows:

- 1) Permanent treatment discontinuation. For this intercurrent event, the data from the period after permanent discontinuation of trial treatment are not included and there will be no imputation of missing data. It is to be noted that for patients in the on demand arm, permanent treatment discontinuation will mean initiation of PPX.
- 2) Temporary treatment discontinuation. For this intercurrent event the 'treatment policy' strategy is used meaning that the data from this period are included.
- 3) Use of factor products not related to treatment of a bleed. For this intercurrent event, the data during this period are not included and there will be no imputation of missing data.
- 4) Minor surgery. For this intercurrent event the 'treatment policy' strategy is used. The definition of minor surgery is outlined in Table 14.

The five components of the estimand for the secondary efficacy endpoints addressing the secondary efficacy objectives are as follows for HA patients:

• Endpoint:

Arm 4 patients who have been on stable PPX for at least 24 weeks in study 4322:

- For previous PPX (study 4322): The number of treated spontaneous or traumatic bleeding episodes from the point in time where PPX is stable and up until the end of study.
- For concizumab PPX (trial 4307): The number of treated spontaneous or traumatic bleeding episodes from the point in time where the concizumab maintenance dose is confirmed, increased or decreased and up until the confirmatory analyses cut-off.

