8.1 Discontinuation of trial treatment

The patient may be discontinued from trial product at any time during the trial at the discretion of the investigator for safety, behavioural, compliance or administrative reasons.

Efforts must be made so that patients, who discontinue trial product, attend and complete all scheduled visit procedures according to the flowchart in Section 2. Patients should stay in the trial irrespective of lack of adherence to the treatment, lack of adherence to visit schedule or missing assessments. Only patients who withdraw consent will be considered as withdrawn from the trial. Patients must be educated about the continued scientific importance of their data, even if they discontinue trial product.

The patient must be discontinued from trial product, if the following applies:

- 1. Included in the trial in violation of the inclusion and/or exclusion criteria
- 2. Simultaneous participation in another clinical trial of an approved or non-approved investigational medicinal product
- 3. Incapacity or unwillingness to follow the trial procedures
- 4. Significant thromboembolic event^a
- 5. Event of Disseminated Intravascular Coagulation (DIC)
- 6. Event of Thrombotic Microangiopathy (TMA)
- 7. Event of severe or serious hypersensitivity reaction related to concizumab

^aThe definition of a significant thromboembolic events is provided in Appendix 5. For venous thromboembolic events where treatment of concizumab has been discontinued, re-initiation of concizumab can be considered by the investigator in the extension part of the trial, after the patient has fully recovered. The investigator must contact and agree with Novo Nordisk before reinitiating concizumab treatment.

See the flowchart in Section 2 for data to be collected at the time of treatment discontinuation and follow-up and for further evaluations that need to be completed.

The primary reason for discontinuation of trial product must be specified in the end-of-treatmentform in the eCRF, and final drug accountability must be performed. A treatment discontinuation session must be made in the IWRS.

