When evaluating the negative binomial analysis (with exposure time as offset, treatment as factor and incorporating within-subject repeated measurements using of an unstructured covariance structure) with respect to showing non-inferiority of concizumab prophylaxis vs previous prophylaxis in a within-patient comparison, the power of showing non-inferiority is at least 79% with a concizumab ABR of 3-5, an ABR for previous prophylaxis of 4, a non-inferiority margin of 2.0 on the relative scale, a sample size of 30, a yearly over-dispersion of 13 and assuming a patient's frailty for experiencing bleeds in the first period (on previous PPX) and the second period (on concizumab PPX) is fully correlated (i.e. a correlation of 1). Other scenarios with different assumptions are displayed in Table 17 below including scenarios where the assumption of a correlation of 1 is lowered to 0.8.

Date: 25 March 2021 Novo Nordisk Version: 5.0 Status: Final

Page:

Final 87 of 138

Table 17 Power to demonstrate non-inferiority separately for patients with HA or HB

			Non-infer	lative scale	
Correlation ^a	ABR on concizumab ABR on previous prophylaxis	1.5	1.8	2.0	
		2	6%	21%	33%
	3	4	95%	99%	>99%
		6	>99%	>99%	>99%
	_	2	~0%	~0%	~0%
1.0	5	4	25%	61%	79%
		6	97%	>99%	>99%
	_	2	~0%	~0%	~0%
	7	4	0%	6%	17%
		6	50%	87%	95%
	_	2	5%	12%	18%
	3	4	66%	83%	89%
		6	96%	99%	>99%
	_	2	~0%	~0%	~0%
0.8	5	4	14%	33%	46%
	6	71%	89%	95%	
	_	2	~0%	~0%	~0%
	7	4	~0%	5%	11%
		6	26%	55%	71%

^a The spearman correlation between a patient's frailty for experiencing bleeds in the first and the second treatment period.

Combined power

Assuming that the confirmatory secondary endpoint is independent of the primary endpoint the combined power becomes at least 82%*79% = 65% for haemophilia A patients and at least 62% for haemophilia B patients.

Expected frequency and pattern of missing data

Since treatment options for haemophilia patients are limited and there is a general tendency to continue with the treatment regimen, the completion rate for this study is expected to be high with less than 15 % withdrawing or discontinuing treatment prematurely. The study will randomise 24 patients with haemophilia A and 36 with haemophilia B to account for potential withdrawals in particular in relation to other endpoints in this trial.

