10.3.2 Secondary endpoints

10.3.2.1 Confirmatory secondary endpoints

The confirmatory secondary endpoint for haemophilia A patients is defined in Section 4.3.2.1.

Only the subset of patients from the FAS that entered the maintenance period in arm 4 and who were on a stable PPX regimen for at least 24 weeks in NN7415-4322 (explorer 6) will contribute to the analysis. The analysis will be done using a negative binomial regression, where the patients' number of bleeds will be analysed with exposure time as offset, treatment and bleeding frequency (<9, ≥9 bleeding episodes during the past 24 weeks prior to screening) as factors and within-subject repeated measurements will be incorporated using of an unstructured covariance structure. The estimated ratio of ABR between the treatment regimens (concizumab prophylaxis versus previous prophylaxis) with corresponding 95% confidence interval and also estimates of the actual ABRs with corresponding 95% confidence intervals in each treatment period will be presented. Non-inferiority will be confirmed if the upper limit of 95% confidence interval is below 2.0.

A similar approach will be used for haemophilia B patients.

Sensitivity analyses

The below sensitivity analyses will be implemented by haemophilia type to further investigate the underlying assumptions of the above statistical analyses. Note that as different strategies are implemented to address some of the intercurrent events, this analysis addresses a slightly different estimand:

- In order to investigate the missing at random (MAR) assumption, a tipping point analysis will be implemented where patients that permanently discontinue concizumab treatment after the dose is decreased, increased or confirmed and before 24 weeks of treatment have been observed will be modelled with an increasing bleeding rate until the conclusion of non-inferiority is changed. For those patients that permanently discontinues treatment before 24 weeks on maintenance dose, the offset period will be fixed at 24 weeks. For any patient that permanently discontinues treatment before the confirmatory analyses cut-off but after 24 weeks on maintenance dose will not be considered to have missing data for the purpose of this tipping point analysis.

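### Raising the bleeding rate of early discontinuers in both arms weakens the primary tipping-point analysis, because the arm 1 increase favours concizumab

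*Protocol*

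**What the plan says.** Protocol Section 10.3.1 (Sensitivity analysis) offers the tipping-point analysis as the check on MAR for the primary endpoint: "patients that permanently discontinue treatment before 24 weeks for arm 1 or before 32 for arm 2 will be modelled with an increasing bleeding rate", continued until the superiority conclusion changes. The offset of these patients is fixed at 24 weeks (arm 1) or 32 weeks (arm 2). Section 10.3 sets the criterion: superiority "will be concluded if the two-sided 95% confidence interval of the treatment ratio is below 1".

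The text does not say whether the arms share one increase or are varied separately, or whether the increase is an added rate or a factor. Section 10.3 states that the SAP "includes a more technical and detailed elaboration of the statistical analyses". The SAP supplied covers the 56-week cut-off only, and its Section 5.3 refers the primary analysis to confirmatory SAP version 5, which was not among the documents.

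Related provisions:
- Section 10.3.2.1, the secondary tipping-point analysis, raises the rate only for "patients that permanently discontinue concizumab treatment after the dose is decreased, increased or confirmed and before 24 weeks of treatment have been observed".
- Section 4.2 notes that "for patients in the on demand arm, permanent treatment discontinuation will mean initiation of PPX".
- Section 10.1 expects "less than 15 % withdrawing or discontinuing treatment prematurely".
- Section 8.1 ("Efforts must be made so that patients, who discontinue trial product, attend and complete all scheduled visit procedures") and a further analysis in Section 10.3.1 ("a model where all intercurrent events will be handled by use of the treatment policy strategy will be fitted") limit the reliance on MAR.

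**The concern.** A tipping-point analysis should make the missing data progressively less favourable to the claim. Raising the rate of arm 2 dropouts does that, because the ratio moves towards 1. Raising the rate of arm 1 dropouts does the opposite. If both are raised together, part of the stress is undone whenever at least one arm 1 patient discontinues before week 24.

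The result at stake is the tipping value itself. A reader will take it as the excess bleeding among concizumab dropouts that the superiority claim can withstand, and under a joint shift it would be too large.

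**Working it through.** **Inputs.** From Section 10.1: on-demand ABR 24 (haemophilia A, HA) and 18 (haemophilia B, HB); concizumab ABR 3 to 5; yearly over-dispersion 13; follow-up 24 and 32 weeks; 24 HA and 36 HB patients randomised, which at 1:2 is 8 against 16 and 12 against 24. Over-dispersion was read as 1 + k × ABR = 13 in each arm.

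**Reproducing the plan's power.** Negative binomial simulation without dropout (12,000 trials per case), at the plan's 7 against 14 (HA) and 11 against 22 (HB), for concizumab ABR 3, 4 and 5:
- HA: 92, 87 and 83%; Table 16 states 91, 87 and 82%.
- HB: 93, 86 and 79%; Table 16 states 92, 86 and 79%.

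**Algebra of the offset.** Let r1 and r2 be the fitted rates and f1 and f2 the shares of planned follow-up that are missing. After filling in, the ratio is:
- added rate δ in both arms: (r2 + f2·δ)/(r1 + f1·δ)
- common factor m in both arms: (r2/r1) × (1 − f2 + f2·m)/(1 − f1 + f1·m)
- arm 2 only: the same numerators, with the denominator left unshifted.

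Illustration with dropouts leaving at half of follow-up and concizumab ABR 4:
- HA, 1 of 8 and 2 of 16: f1 = f2 = 0.0625, so a common factor cancels. The simulated median ratio stayed at 0.143 for factors 5 to 50.
- HB, 2 of 12 and 3 of 24: f1 = 0.0833, f2 = 0.0625. At m = 20, (0.9375 + 1.25)/(0.9167 + 1.6667) = 0.847, and 0.197 × 0.847 = 0.167 (simulated 0.167): the joint shift moves the ratio in favour of concizumab. Arm 2 only gives 0.197 × 2.1875 = 0.431 (simulated 0.432).
- HB, added rate of 100/year: joint (4 + 6.25)/(18 + 8.33) = 0.389; arm 2 only 10.25/18 = 0.569. Simulated medians among significant trials were 0.367 and 0.532. The offset is partial.

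Up to a factor of 50, 78% (HA) and 92% (HB) of these trials never tipped under the joint shift, against 8% and 2% with arm 2 only. Across concizumab ABR 3 to 5 and several discontinuer splits, joint tipped later in 80 to 99% of trials (factor) or 44 to 99% (added rate), and never earlier.

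**Simulation with random dropout, added rate.** There were 12,000 trials per case at the full randomised numbers. Assumptions: the same dropout probability in each arm, uniform dropout time, missing time filled at the expected count from the arm's fitted rate plus the shift, and the bleeding-frequency stratum left out. The shift that returns concizumab dropouts to the on-demand rate is 24 − 3 = 21 or 24 − 5 = 19 (HA) and 18 − 3 = 15 or 18 − 5 = 13 (HB). Entries are for concizumab ABR 3 / 5.

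| Result | Dropout | HA joint | HA arm 2 only | HB joint | HB arm 2 only |
|---|---|---|---|---|---|
| % still superior, return to on-demand | 10% | 96.4 / 95.6 | 95.4 / 93.9 | 97.8 / 97.0 | 96.7 / 95.2 |
| | 15% | 95.3 / 94.1 | 93.3 / 91.5 | 97.2 / 96.0 | 95.1 / 92.9 |
| % still superior, +50/year | 10% | 78 / 75 | 73 / 68 | 75 / 70 | 66 / 59 |
| | 15% | 68 / 66 | 59 / 55 | 63 / 59 | 48 / 42 |
| Median tipping shift, bleeds/year | 10% | 93 / 95 | 67 / 64 | 92 / 91 | 63 / 56 |
| | 15% | 75 / 76 | 55 / 53 | 68 / 65 | 48 / 42 |

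Percentages are of all superior trials. Medians are of superior trials with dropouts in both arms. The gap is 1 to 3 points at the return-to-on-demand shift (under 1 point at 5% dropout). At +50/year it is 5 to 11 points (10% dropout) and 9 to 18 points (15%), computed before rounding.

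**Checks.** Multiple imputation (20 imputations, 2,500 trials per case) gave gaps of 2 to 6 points at the return-to-on-demand shift and, at +50/year, 6 to 12 (10% dropout) and 11 to 20 (15%). A separate run of 500 trials per case at ABR 5 gave median tipping shifts, joint against arm 2 only, of 82 against 58 and 81 against 55 (HA, 10 and 15% dropout) and 112 against 60 and 68 against 42 (HB). The direction is the same, with visible simulation noise.

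**How often there is no offset.** With no arm 1 dropout the two versions coincide. The probability is (1 − p)^8 for HA and (1 − p)^12 for HB. At p = 5, 10 and 15% this gives 66, 43 and 27% (HA) and 54, 28 and 14% (HB).

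**The case against.** The strongest reply is that the sentence may only define who has missing data and with what offset. It never says that the increase is common, and confirmatory SAP version 5 may vary the arms separately. That stands as a limit, so the conclusion is conditional. But both arms sit under one increase with one stopping rule, and nothing in the documents supplied calls for separate shifts.

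Second, interpretation hardly changes. Both sets of median tipping shifts lie well beyond the assumed on-demand rates of 24 and 18, and the gap is small at the one clinically anchored shift. The complete-offset case needs a common factor, which fits poorly with a search that is meant to end in a changed conclusion. This stands too, and it keeps the point at low priority. The less than 15% in Section 10.1 is an overall figure, so equal dropout in each arm is an assumption.

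Third, a joint shift asks a legitimate question: what if dropouts in both arms bleed more than MAR predicts? Arm 1 patients who start prophylaxis may do so after heavy bleeding, and shifting arm 2 alone leaves MAR in arm 1 untested. That is fair against the arm 2-only option; a two-way grid answers it.

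Fourth, the secondary tipping-point analysis is not a strict parallel, because Section 4.2 places patients who stop prophylaxis in study 4322 outside its target population. Accepted; the argument does not rest on that comparison.

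**Conclusion.** The concern holds, conditional on a joint increase. The arm 1 part then works in favour of concizumab, and the reported tipping point overstates the robustness of superiority to departures from MAR among concizumab dropouts. On an added-rate scale the inflation is about 1.4 to 1.6 times in the main simulation, given dropouts in both arms. On a common-factor scale the offset is full when the missing shares are equal and reversed when arm 1 has the larger share. The tipping value is what is distorted; at plausible shifts the superiority verdict rarely changes. The primary test, type I error and power are untouched, and the retention effort and treatment-policy analysis give some protection, the latter for a slightly different estimand. The sizes rest on the plan's rates and over-dispersion and on the assumed dropout pattern.

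**What to change.** In Section 10.3.1, apply the increase only to arm 2 patients who discontinue before week 32 and keep arm 1 early discontinuers at the arm 1 MAR rate; or report a two-way grid with separate shifts by arm, which also tests MAR in arm 1. State whether the increase is an added rate or a factor. Keep the 24- and 32-week offsets. Align confirmatory SAP version 5 if it does not already do this.

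The cost is one sentence in the protocol and, if needed, one in that SAP, with slightly more analysis and no new data. The tipping point may look less favourable. Sections 5.5.1 and 5.5.2 of the 56-week SAP (04 August 2022) describe confirmatory results as already concluded or presented. If the primary analysis has been run, the practical form is a supplementary arm-specific table labelled post hoc.
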